Our secondary aim is to determine whether the intervention affects 1) the frequency of positive-urine tests for opioids and 2) the frequency and proportion of subjects self-reporting opioid use. (We recognize that, due to constraints on in-person follow-up imposed by the COVID-19 pandemic, individuals who are most likely to get urine tests are those who are in treatment and those who might subsequently present to the emergency department (ED) for opioid-related complaints.) Our hypothesis is that our intervention will decrease both. As in the previous aim, data will be collected remotely/electronically from self-report and EPIC. If the sources of information were to conflict, then what is entered in EPIC will take precedence.

Data from our entire cohort will be compared in aggregate with patients who were started on BUP in the ED over the same time period and with historic controls who received only printed resources addressing OUD as reported in [name] et al.¹¹

2. Probable Duration of Project: State the expected duration of the project, including all follow-up and data analysis activities.

The probable duration of the project is 2 years (from 09/2019-09/2021). There is potential for extension after this time, depending on availability of funding.

3. Background: Describe the background information that led to the plan for this project. Provide references to support the expectation of obtaining useful scientific data.

Importance of problem.

The epidemic of opioid use disorder (OUD) prompted a presidential declaration of a public health emergency in October, 2017, and it was extended in January, 2018.² In 2016, an unprecedented 63,632 deaths in the United States (US) were attributed to drug overdose; 2/3 of these involved opioids.³ The deaths due to drug overdose in 2016⁴ exceeded the number of traffic fatalities during the peak year of 1972,⁵ the number of HIV deaths at their peak in 1995, the final year before the introduction of triple antiviral therapy,⁶ and the peak year for gun violence in the US, which was 1993.^{7,8} Nonfatal opioid overdoses are highly associated with ongoing OUD and recurrent overdoses. One study reviewing emergency medical service (EMS) records of

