3. Screen positive for OUD using mini international neuropsychiatric interview (MINI) (if applicable)	+	-
4. At least 1 opioid overdose requiring resuscitation by naloxone	+	-
5. Have a non-opioid overdose explanation for decreased level of consciousness, miosis, or decreased respiratory rate (if applicable)	-	+
6. Positive for OUD using a health questionnaire containing questions about prescription opioid and heroin use	+	-
7. Not in a critically ill state at the time of consent (e.g., not actively suicidal, psychotic, septic, and/or experiencing cardiac arrest)	+	-
8. 3.,4., & 6. (in this column) must have occurred within ≤ 7 days (inclusive) from date of consent if the prospective participant were immediately discharged from the emergency department (ED), floor, or other health care facility; consent may be obtained at any of these locations	+	-
9. Homicidal	-	+
10. Able to consent to program/study participation	+	-
11. Permanent residence is a long-term care/skilled nursing facility	-	+
12. Simultaneously enrolled in another study whose principal investigator (PI) or co-PI is a faculty member in the Department of Emergency Medicine	-	+
13. Prescribed opioids for acute pain, chronic pain, or palliative care without OUD	-	+
14. Stably enrolled in opioid agonist treatment or other medication-assisted therapy for OUD at the time of consent	-	+
15. In police custody or incarcerated (at the time of consent to participate or any known time after). (Parolees & those on probation may be eligible, but are NOT the target population and may be enrolled only incidentally .)	-	+
16. Refused buprenorphine/naloxone (BUP), if offered	+	-
17. Has a mailing address or P.O. box	+	-
18. Able to answer questions electronically/remotely (including by phone)	+	-

8. How will **eligibility** be determined, and by whom? *Write here*

In general, eligibility will be determined by the RCP team. ED and study staff may assist occasionally.

9. **Risks:** Describe the reasonably foreseeable risks, including risks to subject privacy, discomforts, or inconveniences associated with subjects participating in the research.

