We estimate that data from approximately 100 individuals will be used. Recent data from American Medical Response (AMR) suggest that in 2017, 447 individuals have been transported to the YNHH ED for heroin overdose, and 136 others were documented as being treated in the ED. We expect that many of these individuals will elect to undergo BUP treatment in the ED, but that many others will enroll in our research. However, inevitably some will be lost to follow up. Power calculations are based on previously published data involving screening, brief intervention, and referral to treatment and the use of buprenorphine in primary care settings.^{1,32,43} Findings suggest small-to-moderate ($f=0.2-0.4$) and moderate ($f=0.5$), respectively, effect sizes for these practices. Statistical power ($1-\beta$) will be 80%, and significance level (α) will be 5%.

SECTION II: RESEARCH INVOLVING DRUGS, BIOLOGICS, RADIOTRACERS, PLACEBOS AND DEVICES

If this section (or one of its parts, A or B) is not applicable, check off N/A and delete the rest of the section.

A. RADIOTRACERS

N/A

1. Name of the radiotracer: *Write here*
2. Is the radiotracer FDA approved? YES NO

If NO, an FDA issued IND is required for the investigational use unless RDRC assumes oversight.

3. Check one: IND# *Write here* or RDRC oversight (RDRC approval will be required prior to use)
4. **Background Information:** Provide a description of previous human use, known risks, and data addressing dosage(s), interval(s), route(s) of administration, and any other factors that might influence risks. If this is the first time this radiotracer is being administered to humans, include relevant data on animal models.
Write here
4. **Source:** Identify the source of the radiotracer to be used. *Write here*
5. **Storage, Preparation and Use:** Describe the method of storage, preparation, stability information, method of sterilization and method of testing sterility and pyrogenicity.
Write here

B. DRUGS/BIOLOGICS

N/A

1. If an **exemption from IND filing requirements** is sought for a clinical investigation of a drug product that is lawfully marketed in the United States, review the following categories and complete the category that applies (and delete the inapplicable categories):

Exempt Category 1: The clinical investigation of a drug product that is lawfully marketed in the United States can be exempt from IND regulations if all of the following are yes:	

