A YNHH New Product/Trial Request Form must be completed via EPIC: Pull down the Tools tab in the EPIC Banner, Click on Lawson, Click on “Add new” under the New Technology Request Summary and fill out the forms

requested including the “Initial Request Form,” “Clinical Evidence Summary”, and attach any other pertinent documents. Then select “save and submit” to submit your request; AND

Your request must be reviewed and approved **in writing** by the appropriate YNHH committee before patients/subjects may be scheduled to receive the investigational device or investigational procedure.

2. **Background Information:** Provide a description of previous human use, known risks, and any other factors that might influence risks. If this is the first time this device is being used in humans, include relevant data on animal models.

Write here

3. **Source:**

- a) Identify the source of the device to be used. *Write here*
b) Is the device provided free of charge to subjects? Yes No

4. **Investigational device accountability:** State how the PI, or named designee, ensures that an investigational device is used only in accordance with the research protocol approved by the HIC, and maintains control of the investigational device as follows:

- a) Maintains appropriate records, including receipt of shipment, inventory at the site, dispensation or use by each participant, and final disposition and/or the return of the investigational device (or other disposal if applicable): *Write here*
b) Documents pertinent information assigned to the investigational device (e.g., date, quantity, batch or serial number, expiration date if applicable, and unique code number): *Write here*
c) Stores the investigational device according to the manufacturer's recommendations with respect to temperature, humidity, lighting, and other environmental considerations: *Write here*
d) Ensures that the device is stored in a secure area with limited access in accordance with applicable regulatory requirements: *Write here*
e) Distributes the investigational device to subjects enrolled in the IRB-approved protocol: *Write here*

SECTION III: RECRUITMENT/CONSENT AND ASSENT PROCEDURES

1. **Targeted Enrollment: Give the number of subjects:**

- a. Targeted for enrollment at Yale for this protocol: 100 participants total
b. If this is a multi-site study, give the total number of subjects targeted across all sites: N/A

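### Two primary outcomes at two time points share a single 5% significance level, with no ranking, success rule or adjustment

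*Combined protocol and SAP*

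**What the plan says.** Section I, item 12 (Statistical Considerations) lists two primary outcomes: the percentage of individuals with a repeat opioid overdose needing naloxone, and the percentage in treatment or in remission. Both are recorded at baseline, 30 days and 180 days. The statement of aims at the start of Section I asks about engagement or remission at both follow-up times. The Research Plan (item 4) states the hypothesis as fewer overdoses and more remission, joined by a plain 'and'.

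The planned test is a 2-df chi-square across three groups: the intervention cohort, patients started on BUP in the ED, and historical controls. The aims describe the comparison this way: "Data from our entire cohort will be compared in aggregate with patients who were started on BUP in the ED", and add the historical group.

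The sample-size paragraph of item 12 says "We estimate that data from approximately 100 individuals will be used". It cites published effects of f = 0.2-0.4 and 0.5 ("respectively, effect sizes for these practices") and then states power and alpha without conditions (power "will be 80%, and significance level" 5%). On attrition it says "However, inevitably some will be lost to follow up" and gives no rate. Section III, item 1 reads "Targeted for enrollment at Yale for this protocol: 100 participants total".

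**The concern.** Two outcomes at two follow-up times make four candidate primary tests. One alpha is given, and no text says which test, or which combination, decides whether the trial succeeded. Nothing would then prevent whichever of the four comparisons turned out significant from being reported as the primary result. The groups are not randomised and one comparator is historical, so a primary test fixed in advance is one of the few protections the design can offer against selective reporting.

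The power statement has a related gap. A reader cannot tell which outcome, effect or group sizes the 80% refers to, and so cannot tell what the study was sized to detect.

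**Working it through.** **1. The plan's own figure.** Inputs from item 12: about 100 individuals, alpha 5%, power 80%, 2-df chi-square, effects 0.2-0.4 and 0.5. I read the printed f as Cohen's w, which is a matter of notation. Power comes from the noncentral chi-square with noncentrality λ = N·w². For 80% power at 5%, λ = 9.635, so N = 9.635/w².

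| w | Total N for 80% | Power at total N = 100 |
|---|---|---|
| 0.2 | 241 | 42% |
| 0.3 | 108 | 77% |
| 0.4 | 61 | 96% |
| 0.5 | 39 | 99.7% |

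A total of 100 gives 80% power at w = √(9.635/100) = 0.31. That lies inside the quoted range but is not stated in the plan. The 80% is therefore neither reproduced nor contradicted.

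**2. What the 100 refers to.** The text favours the intervention cohort alone. The sample-size paragraph expects many patients to choose BUP in the ED, "but that many others will enroll in our research". Inclusion criterion 16 is "Refused buprenorphine/naloxone (BUP), if offered". The ED-BUP patients are described as a separate comparison group. Power then depends on comparator sizes that the documents do not give. With assumed totals:

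- Total 200: power at w = 0.2 is 72%; smallest w for 80% is √(9.635/200) = 0.22.
- Total 300: power at w = 0.2 is 88%; smallest w is √(9.635/300) = 0.18.
- At w = 0.3 or more, power is at least 97% for either total.

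**3. Any one of four tests counts.** Each test is at 5% and all four nulls are true.

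- Independent: 1 − 0.95⁴ = 0.185.
- Upper bound under any dependence: 4 × 0.05 = 0.20.
- Simulated with dependence: 0.159-0.180. Assumptions: 100 per group; overdose 10% by 30 days, nested in 15-30% by 180 days; engagement 40%; latent between-time correlation 0.2-0.9; 40,000 runs. Testing each at 1.25% brings this to 0.041-0.046.

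**4. Both outcomes required, either time point counts.** Suppose one outcome is null and the other truly differs and is almost sure to be significant. The false success rate is then that of two tests on the null outcome: 1 − 0.95² = 0.0975 if independent, bound 0.10. Simulated values are 0.079-0.089 for overdose and 0.091-0.099 for engagement.

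**5. Price of a rule.** Holm's first step uses 0.05/4 = 0.0125, where 80% power needs λ = 13.305. At an assumed total of 300 and w = 0.2, λ = 300 × 0.04 = 12. Power is 88% at 5% and 75% at 1.25%. Requiring both outcomes at one time point, each at 5% with 88.3% power, gives 0.883² = 78% if independent and at least 2 × 0.883 − 1 = 77%.

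**6. Unequal comparators.** The Background (How this project will improve scientific knowledge) says continued engagement on BUP is about twice that after a brief interview or community referral. Take assumed rates of 20% (intervention), 40% (ED-BUP) and 20% (historical), 100 each. The mean is 26.67%, so w² = [(0.0667² + 0.1333² + 0.0667²)/3]/(0.2667 × 0.7333) = 0.0455. Hence w = 0.21 and λ = 13.6. The 2-df test rejects about 92% of the time although the intervention does no better than the historical group.

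**The case against.** The plan does not say that any one of four significant tests would be called success, and the 'and' in the hypothesis can be read as requiring both outcomes. That is fair: 18.5% is what the silence permits, not what the plan commits to. But the 'and' reading names no time point, and step 4 shows that up to about 10% remains under it.

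The 18.5% also assumes that all groups are equal on every outcome. By the plan's own account that is not expected for engagement, where ED-BUP and the historical group should differ. This stands, and it limits both the figure and the remedy. A multiplicity rule controls how often the three-group test is wrongly significant; it cannot attribute a significant engagement result to the intervention. The overdose outcome is less affected.

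A reader might infer that the trial is underpowered, or that 100 participants and 80% power is a miscalculation. The documents do not support that. The low figures of 42% and 77% need 100 to be the total across all groups, which is the less likely reading, and even then an effect of 0.31 inside the quoted range gives 80%. If 100 is the intervention cohort, power may be ample. The investigators may also know the historical group's size from the publication that defines it.

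Loss to follow-up should not be applied across the board either. Repeat overdose is identified from the hospital record, so a missed contact need not remove a participant from that outcome.

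**Conclusion.** The multiplicity gap holds. With two primary outcomes, two time points, one 5% alpha and no rule, the false-positive risk reaches 18.5% (independent tests, all nulls true, any one test counting) and cannot exceed 20%. It is up to about 10% for a null outcome if both outcomes are needed but either time point will do. These figures rest on the stated success rules, which are assumptions because the plan gives none.

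The power statement is a reporting gap and not an arithmetic error. The 80% cannot be verified, because no effect is selected, group sizes are not stated and no loss allowance is given. Nothing in the documents shows it to be false.

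**What to change.** State one primary decision rule in item 12, before outcome data are examined:

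- (a) name one primary outcome at one time point. The other three tests become secondary, and power for the named test is unchanged; or
- (b) keep all four as primary and apply Holm. At the assumed total of 300 and w = 0.2, first-step power falls from 88% to 75%; or
- (c) if both outcomes must succeed, say so and name one time point, testing each outcome at 5%. Joint power in the same example is about 78% if the outcomes are independent, and at least 77%.

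In the sample-size paragraph, say whether 100 is the intervention cohort or the total. Give the analysed size of each group, the effect and outcome that the 80% refers to, and a loss allowance for outcomes that need follow-up contact. If 100 is the total, say that 80% holds only for w of at least 0.31. For engagement, give an assumed rate for each of the three groups instead of one common comparator rate, so that the stated power is not driven by the difference between ED-started BUP and the historical group.

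These are text changes only and need no extra enrolment. The cost is the loss of primary status or of power shown under each option.

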
Follow up	No Intervention	PRIDE Intervention	p-value	% Change with Intervention
days since enrollment of intervention	participants with ≥ 1 unplanned health care encounter total participants		—	—
30 days	$\frac{429}{1759}$ (24%)	$\frac{373}{2841}$ (13%)	<0.001	-46
90 days	$\frac{520}{1327}$ (39%)	$\frac{613}{2352}$ (26%)	<0.001	-33

Table 1. Unplanned health care encounters with vs. without PRIDE intervention. For the “No Intervention group,” “follow up” refers to the number of days following enrollment; for the “Intervention group,” it refers to the 30-90 days following intervention.

Follow up	No Intervention	PRIDE Intervention	p-value	% Change with Intervention
days since enrollment of intervention	participants with ≥ 1 unplanned health care encounter total participants		—	—
30 days	$\frac{156}{980}$ (16%)	$\frac{100}{1285}$ (8%)	<0.001	-50
90 days	$\frac{174}{652}$ (27%)	$\frac{162}{980}$ (17%)	<0.001	-37

Table 2. EMS utilization among enrollees with vs. without PRIDE intervention. For the “No Intervention group,” “follow up” refers to the number of days following enrollment; for the “Intervention group,” it refers to the 30-90 days following intervention.

Proposed adaptation of PRIDE to serve persons with OUD.

We propose to adapt the PRIDE program infrastructure to provide a safety net for patients who 1) have been resuscitated from an opioid overdose with naloxone, 2) have screened positive for OUD using the MINI^{29,30}

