
- d. For multi-site studies for which the Yale PI serves as the lead investigator: N/A
 - i. How will adverse events and unanticipated problems involving risks to subjects or others be reported, reviewed and managed? N/A
 - ii. What provisions are in place for management of interim results? N/A
 - iii. What will the multi-site process be for protocol modifications? N/A

12. **Statistical Considerations:** Describe the statistical analyses that support the study design.

Study design

Primary outcomes

The primary outcomes will be 1) percentage of individuals with repeat opioid overdose events requiring naloxone resuscitation, identified using YNHH's electronic medical record system (EPIC), and 2) percentage of individuals engaged in any treatment for OUD or who are in remission. Data will be recorded at baseline and at 30 and 180 days after consent to participate in the research.

Secondary outcomes

The secondary outcomes will be 1) frequency and percentage of individuals with positive opioid tests (urine) recorded in their hospital charts or during medication program monitoring, and 2) frequency and percentage of subjects with self-reported opioid use. Data will be recorded at baseline and at 30 and 180 days after consent to participate in the research.

Statistical analyses

We will document demographics (sex, race/ethnicity, age, education, employment status, etc.) and clinical characteristics (e.g., heroin use, non-opioid use in the past 6 months, lifetime treatment for addiction etc.) among all cohorts. χ^2 tests (2 df) will be employed to detect statistically significant differences.

Group	X	No X	Total
PRIDE + CCAR intervention			
BUP-initiated in ED after OD			
Historical control(s)			
Total			

For primary outcomes, "X" is % of repeated overdose events or % of treatment engagement. For secondary outcomes, "X" is frequency or % positive testing for opioid tests or % (self-reported) opioid abuse.

Sample size determination

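### The blanket 80% power figure is not supported for primary outcome 1 (repeat naloxone-treated overdose), and on about 100 individuals power for a halving is well below 80% unless repeat overdose is common or the comparator groups are large

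*Combined protocol and SAP*

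**What the plan says.** Section I, item 12 (Statistical Considerations) names two binary primary outcomes. The first is the "percentage of individuals with repeat opioid overdose events requiring naloxone resuscitation", found in EPIC. The second is the percentage engaged in treatment or in remission. Both are recorded at 30 and 180 days and compared by 2-df chi-square across three groups: the RCP intervention, patients started on buprenorphine in the ED, and historical controls.

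Under Sample size determination the plan says "We estimate that data from approximately 100 individuals will be used". Section III, item 1 sets the enrolment target at "100 participants total". The inputs are described as follows: "Power calculations are based on previously published data involving screening, brief intervention, and referral to treatment and the use of buprenorphine in primary care settings". The effect sizes are given as "Findings suggest small-to-moderate ($f=0.2-0.4$) and moderate ($f=0.5$), respectively, effect sizes for these practices". Power "will be 80%, and significance level (α) will be 5" percent.

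Neither outcome is attached to this statement. The plan gives no expected rate or target difference for either outcome and no size for either comparator. It expects some loss to follow-up but puts no figure on it.

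**The concern.** Reducing subsequent overdose is the first aim and part of the main hypothesis, yet the only power statement draws on effects of other practices. Those effects are printed as f values and are not linked to any overdose rate. The three references cited for them are, by title, a recovery-capital instrument paper, a trial of counselling with buprenorphine-naloxone, and a tobacco-dependence trial. None names overdose as its subject.

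An unqualified 80% suggests that a useful reduction in overdose would probably be detected. If true power is far lower, a non-significant chi-square at 30 or 180 days is likely even when the RCP team works. A reader relying on the printed 80% could then conclude that it does not. With few events, a small chance imbalance could also be over-read in either direction.

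**Working it through.** **Inputs from the documents.** N about 100, two-sided by nature (chi-square), 2 df, alpha 0.05, power 80%, f = 0.2–0.4 and 0.5. Group sizes are not stated, nor whether the 100 is the intervention cohort or all three groups.

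**Assumptions, because the documents give no figure.** Repeat-overdose risk in the comparators is 10%, 20% or 30%, the same in both. The RCP team reduces it by 33% to 50%. That span is borrowed from the PRIDE reductions in Tables 1 and 2 (33% to 50%), which concern unplanned health care and EMS use in older people, not overdose. f is read as the chi-square effect size w.

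**Step 1: the plan's own figure.** Power depends on the non-centrality λ = N·w². For 2 df and alpha 0.05, 80% power needs λ = 9.635.

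- Required total N = 9.635 / w²: about 241 (w = 0.2), 107 (0.3), 60 (0.4), 39 (0.5).
- Power at N = 100: 41.5% (0.2), 77.1% (0.3), 95.7% (0.4), 99.6% (0.5).
- Effect giving 80% at N = 100: w = √(9.635/100) = 0.310.
- Effect giving 80% at N = 300 (100 per group): w = √(9.635/300) = 0.179.

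No quoted effect size gives a total of 100. Reading f as a three-group ANOVA effect changes little (about 244, 110, 63 and 42). A two-group reading of f = 0.2 as a standardised difference of 0.4 gives 99 per arm, which matches only if 100 means per arm.

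**Step 2: what a halving of overdose amounts to.** For equal groups, w² = mean of (pᵢ − p̄)² / [p̄(1 − p̄)].

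- 5% v 10% v 10%: p̄ = 0.0833; w² = 0.000556 / 0.0764 = 0.00727; w = 0.085.
- 10% v 20% v 20%: p̄ = 0.1667; w² = 0.002222 / 0.1389 = 0.0160; w = 0.126.
- 15% v 30% v 30%: p̄ = 0.25; w² = 0.005 / 0.1875 = 0.0267; w = 0.163.

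All three lie below 0.2, the smallest effect the plan quotes, and below the 0.179 needed even with 100 per group.

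**Step 3: power for outcome 1.** Simulated Pearson 2-df chi-square; order of groups is RCP / buprenorphine / historical.

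| Layout | Reduction | 10% risk | 20% risk | 30% risk |
|---|---|---|---|---|
| 34/33/33 | 33% | 6% | 10% | 14% |
| 34/33/33 | 50% | 8% | 18% | 30% |
| 100/100/100 | 33% | 12% | 22% | 36% |
| 100/100/100 | 50% | 23% | 50% | 75% |
| 100/200/200 | 33% | 11% | 24% | 41% |
| 100/200/200 | 50% | 24% | 56% | 82% |

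At 34/33/33 with a halved 10% risk, about 8 events are expected in the whole study (34 × 0.05 + 66 × 0.10 = 8.3). Complete elimination of a 10% risk gives 26% power there.

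**Step 4: when 80% is reached for a halving.** If the 100 is the total, the comparator risk must be about 65%. With 100 per group it must be roughly 35% (75% power at 30%, 84% at 35%). At 100/200/200 it is reached near 30%.

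**Step 5: dropping the equal-comparator assumption.** If RCP and buprenorphine patients both have half the historical-control risk, power is 21% (34/33/33), 55% (100 per group) and 80% (100/200/200) at a 20% control risk. At 30% it is 33%, 77% and 96%.

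**The case against.** The strongest reply is that the documents never say how common repeat overdose is, so low power cannot be proved from them. That stands. A reader might infer that the outcome is simply too infrequent for 80% power. The documents do not support this: they give no 30- or 180-day rate, and the Background stresses that overdoses recur (62% of one series of fatal cases had been treated for an earlier overdose). That is not a usable rate, but it is no evidence of infrequency.

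A reader might also infer that power falls short on every reading. It does not. Both comparators lie outside the enrolled cohort, so the enrolment target of 100 may be the RCP group alone. Item 12 cites 447 + 136 = 583 overdose patients in one year and expects many to choose buprenorphine, so nothing caps a comparator at 100. A halving at 30% risk then gives 82% at 100/200/200. The Background also associates buprenorphine with lower overdose risk than brief interview or referral. Unequal comparator risks raise power of the three-group test, though the result may then reflect buprenorphine against historical controls rather than the RCP team.

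Nor is this a contradiction between printed figures: the required w of 0.31 lies inside the quoted 0.2–0.4. It is a missing justification.

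None of these replies supplies a calculation for overdose. At 10% or 20% risk with equal comparators, every layout in the table stays below 60%.

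**Conclusion.** The point holds as a claim without support, not as a proven shortfall in all circumstances. The printed 80% has no overdose rate, target reduction or group size behind it for primary outcome 1. Assuming a 10% to 30% comparator risk, equal in both comparators and halved by the RCP team, power is about 8–30% if 100 is the total, 23–75% with 100 per group and 24–82% at 100/200/200. It reaches 80% only in these cases:

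- repeat overdose is common (roughly 35% with 100 per group, about 65% if 100 is the total);
- the comparators are large and the risk is near 30%;
- the comparators are large and buprenorphine patients also have a much lower risk.

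Loss to follow-up in outcome ascertainment would lower these figures, and cumulative events at day 30 cannot exceed those at day 180.

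It would be tempting to conclude that the 80% belongs to outcome 2. The documents do not support that either. No rate or difference is given for it, and if 100 is the total, power is 41.5% at 0.2 and 77% at 0.3, both within the quoted range. If 100 means per group, an effect of 0.2 would be adequately covered (241 needed, 300 available), so the answer turns on a definition the plan leaves out.

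**What to change.** In item 12, Sample size determination, replace the single 80% statement with one power statement per primary outcome. Each should say what the 100 covers and give the size of each comparator group, the assumed rate in each group, and the expected loss to follow-up.

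For primary outcome 1:

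- print power over an assumed range of 180-day risks, for example 10%, 20% and 30% with a 33–50% reduction, and state that 80% is not assured;
- report the risk difference between the RCP group and each comparator with a 95% confidence interval;
- state that a non-significant chi-square will not be taken as evidence of no effect on overdose.

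Do not reassign the 80% to outcome 2 unless it has been calculated for that outcome.

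The cost is a few sentences and a less favourable stated power. No added enrolment, staff or procedures are needed.
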